### *Questionnaire*

The primary source of data on symptoms, functionality, arm use and quality of life will be derived from a questionnaire completed at each lymphedema assessment. Patients who are enrolled in the study will complete the questionnaire at their initial point of enrollment (after diagnosis and prior to definitive breast surgery), and at all subsequent assessments.

This questionnaire is currently being utilized as part of Partners' Protocols 08-540 and DFHCC Protocol #08-308 and as such has been completed by over 500 patients on protocol since 2009. It was developed to analyze symptoms, functionality, fear avoidance behavior, and quality of life. This questionnaire is referred to as the Lymphedema Evaluation Following Treatment for Breast Cancer Questionnaire (LEFT-BC), and it has been pilot tested for clarity, readability, and validity. This pilot testing was completed with a sample of 20 patients currently undergoing perometer measurements as a standard of care within the MGH Gillette Breast Center. After completion of the pilot, adjustments were made to the questionnaire to increase clarity and readability. The complete questionnaire is included in Appendix 2.

In order to minimize respondent burden the questionnaire was limited to 6 written pages and took between 5-12 minutes to complete during the pilot study. We will utilize tablet style PCs for questionnaire completion within the clinic. [name] and [name], MS developed the LEFT-BC Questionnaire program by formatting the

questionnaires for the tablet PCs, and a corresponding database for data logging. The questionnaires will be completed by patients in a point and click manner. In the event that tablet PCs are not available, paper copies of the questionnaire will be available for participant visits. Questionnaire responses from paper based questionnaires will be manually entered into the database.

#### *Risk Assessment*

At each lymphedema assessment, patients will be verbally asked a short series of questions to provide further information for an analysis of the risk factors involved in the development of lymphedema (see Appendix 3). These questions include: number of blood draws, blood pressures, or injections on the affected arm since the last lymphedema assessment. Also recorded is the number of flights, total hours in flight, and whether a sleeve was worn while flying since the last lymphedema assessment.

#### 5.3 Description of Intervention

Results of assessment with BIS will be blinded such that only a  $\geq 5\%$  RVC measured using the perometer will be considered indicative of lymphedema. If at any time while enrolled in this study a patient is detected to have an  $RVC \geq 5\%$  by perometry, a verification measurement including assessment with perometry, BIS, and the LEFT-BC questionnaire will be conducted at a 4-8 week interval. If at this time the patient's RVC measured by perometry is confirmed above 5%, the patient will be offered enrollment into the DFHCC 08-308 Intervention Protocol and/or referred to a clinician for appropriate care. Patients that enroll into Protocol #08-308 will continue to be measured using BIS at the time of each assessment as required by the protocol. Patients that refuse enrollment into the intervention protocol will remain in the current study.

#### 5.4 Data Collection

Patients will be assessed pre-operatively, at the initiation and conclusion of each type of treatment (surgery, chemotherapy and radiation), and every 4-12 months following the completion of treatment for a period of 24 months. Subsequently they will be assessed at the time their follow-up appointments with their oncologists, with no more than 20 months between measurements. At the time of each assessment, the patient will be measured with the perometer, bioimpedance spectroscopy, and will complete the LEFT-BC questionnaire. Data collected at each visit includes arm volume measurements obtained via perometry and quantified using the RVC equation, bioimpedance ratios collected via BIS, self-reported symptoms obtained via the LEFT-BC questionnaire.

#### 5.5 Description of Study Process

The proposed study will incorporate the use of bioimpedance spectroscopy (BIS) to evaluate its validity for detecting and monitoring lymphedema. Patients will be assessed for lymphedema in a prospective manner using perometry, BIS, and the LEFT-BC questionnaire, accruing a total of 200 patients in 5 years. The entire study will be

completed at the MGH main campus, and all patients who present for a baseline (pre-operative) arm measurement and meet the eligibility criteria will be offered the opportunity to participate in this trial. At this time the purpose of the trial will be explained, and any patient that wishes to participate will be assessed using the perometer, BIS, and provided with the LEFT-BC questionnaire to complete prior to surgery. Patients who do not wish to participate in the proposed trial will be asked to participate instead in Partners Protocol #2008P-000540, which involves regular assessment with the perometer and completion of the LEFT-BC questionnaire at the time of each perometer measurement.

#### 5.5.1 Instrument Administration

The perometer, bioimpedance spectroscopy (BIS) device, and the LEFT-BC questionnaire will all be administered by a Lymphedema Studies Clinical Research Staff. Patients will be notified upon arrival to the clinic that they will undergo a lymphedema assessment on that date using the perometer, BIS, and LEFT-BC questionnaire. Perometry measurements will be conducted in a room specifically allocated for its use, and require about 5-10 minutes for completion. BIS assessments will be conducted in a clinical room and require 2-3 minutes to complete. The LEFT-BC questionnaire will be administered on a tablet PC in a clinical room or given as a paper copy for the patient to complete in the event that tablet PC's are not available. The questionnaire takes 5-12 minutes to complete.

#### 5.5.2 Intervention Administration

As stated previously, results of assessment with BIS will be blinded. Patients that experience a  $\geq 5\%$  RVC determined by measurement with perometry and maintain a  $\geq 5\%$  RVC at the 4-8 week verification measurement will be eligible for enrollment into DFHCC Protocol #08-308 Intervention Trial. These patients will continue to be measured using BIS at the time of each assessment as required by the protocol, and intervention will be administered as dictated by DFHCC Protocol #08-308. Patients that refuse enrollment into the intervention protocol will be referred to a clinician for appropriate care and will remain on the current study.

#### 5.5.3 Special Concerns

Please see sections 5.6.2 and 5.6.3 for anticipated reactions and resolution strategies.

#### 5.5.4 Compensation

No compensation is considered.

### **5.60 Adverse Reactions and their Management**

#### 5.6.1 Reporting Adverse or Unanticipated Events

Adverse event collection and reporting is a routine part of every clinical trial. This study will use the descriptions and grading scales found in the NCI Common Terminology

Criteria for Adverse Events version 3.0 (CTCAE v3.0) that is available at  
<http://ctep.cancer.gov/reporting//ctc.html>.

Information on all adverse events, whether reported by the participant, directly observed, or detected by physical examination, laboratory test or other means, will be collected, recorded, followed and reported as described in the following sections.

Adverse events experienced by participants will be collected and reported from initiation of treatment, throughout the study, and within 30 days of the last follow-up visit. Participants who experience an ongoing adverse event or related to a study procedure beyond 30 days will continue to be contacted by a member of the study team until the event is resolved, stabilized, or determined to be irreversible by the participating investigator. Participants should be instructed to report any serious post-study event(s) that might reasonably be related to participation in this study. The investigator should notify the IRB and any other applicable regulatory agency of any unanticipated death or adverse event occurring after a participant has discontinued or terminated study participation that may reasonably be related to the study.

- Adverse Event (AE)

An adverse event (AE) is any undesirable sign, symptom or medical condition or experience that develops or worsens in severity after starting the first dose of study treatment or any procedure specified in the protocol. For the purpose of this study we will be defining adverse events as any of the following that pertain to the patient's breast cancer-related lymphedema:

- Psychological distress caused by heightened awareness of lymphedema and the potential of developing the condition

- Serious adverse event (SAE)

A serious adverse event (SAE) is any adverse event, occurring at any dose and regardless of causality that:

- Results in death
- Is life-threatening. Life-threatening means that the person was at immediate risk of death from the reaction as it occurred, i.e., it does not include a reaction which hypothetically might have caused death had it occurred in a more severe form.
- Requires or prolongs inpatient hospitalization
- Results in persistent or significant disability/incapacity.
- Is a congenital anomaly or birth defect; or jeopardizes the participant and requires medical or surgical intervention to prevent one of the outcomes listed above.

Events **not** considered to be serious adverse events are hospitalizations for:

- routine treatment or monitoring of the studied indication, not associated with any deterioration in condition, or for elective procedures
- elective or pre-planned treatment for a pre-existing condition that did not worsen
- emergency outpatient treatment for an event not fulfilling the serious criteria outlined above and not resulting in inpatient admission
- respite care

• Expectedness

Adverse events can be 'Expected' or 'Unexpected.'

○ Expected adverse event

Expected adverse events are those that have been previously identified as resulting from administration of the agent. For the purposes of this study, an adverse event is considered expected when it appears in the current adverse event list, the Investigator's Brochure, the package insert or is included in the informed consent document as a potential risk.

Refer to Section 6.1 for a listing of expected adverse events associated with the study agent(s).

○ Unexpected adverse event

For the purposes of this study, an adverse event is considered unexpected when it varies in nature, intensity or frequency from information provided in the current adverse event list, the Investigator's Brochure, the package insert or when it is not included in the informed consent document as a potential risk.

• Attribution

Attribution is the relationship between an adverse event or serious adverse event and the study treatment. Attribution will be assigned as follows:

- Definite – The AE is clearly related to the study treatment.
- Probable – The AE is likely related to the study treatment.
- Possible – The AE may be related to the study treatment.
- Unlikely - The AE is doubtfully related to the study treatment.

- Unrelated - The AE is clearly NOT related to the study treatment.

#### 5.6.1.1 Procedures for AE and SAE Recording and Reporting

Reporting participating investigators will assess the occurrence of AEs and SAEs at all participant evaluation time points during the study.

All AEs and SAEs whether reported by the participant, discovered during questioning, directly observed, or detected by physical examination, laboratory test or other means, will be recorded in the participant's medical record and on the appropriate study-specific case report forms.

The descriptions and grading scales found in the CTEP Active Version of the NCI Common Terminology Criteria for Adverse Events (CTCAE) will be utilized for AE reporting. The CTEP Active Version of the CTCAE is identified and located on the CTEP website at:

[http://ctep.cancer.gov/protocolDevelopment/electronic\\_applications/ctc.htm](http://ctep.cancer.gov/protocolDevelopment/electronic_applications/ctc.htm).

All appropriate treatment areas should have access to a copy of the CTEP Active Version of CTCAE.

#### 5.6.1.2 Reporting Requirements

Each investigative site will be responsible to report SAEs that occur at that institution to their respective IRB. It is the responsibility of each participating investigator to report serious adverse events to the study sponsor and/or others as described below.

##### 5.6.1.3 Reporting to the Study Sponsor

N/A. Single site study.

##### 5.6.1.4 Serious Adverse Event Reporting

All serious adverse events that occur after the initial dose of study treatment, during treatment, or within 30 days of the last dose of treatment must be reported to the DF/HCC Overall Principal Investigator on the local institutional SAE form. This includes events meeting the criteria outlined in Section 11.1.2, as well as the following:

- Grade 2 (moderate) and Grade 3 (severe) events that are unexpected and at least possibly related/associated with the intervention.

- All Grade 4 (life-threatening or disabling) events that are unexpected or not specifically listed in the protocol as not requiring reporting.
- All Grade 5 (fatal) events while the participant is enrolled and actively participating in the trial OR when the event occurs within 30 days of the last study intervention.

Note: If the participant is in long term follow up, report the death at the time of continuing review.

#### 5.6.1.5 Non-Serious Adverse Event Reporting

Non-serious adverse events will be reported to the DF/HCC Overall Principal Investigator on the toxicity Case Report Forms.

#### 5.6.1.6 Reporting to the Institutional Review Board (IRB)

Each adverse event will be assessed to determine if it meets the criteria for serious adverse event. If a serious adverse event occurs, expedited reporting will follow local policies, and federal guidelines and regulations as appropriate. It is the responsibility of the participating investigator to notify the Principal Investigator (or Protocol Chair), IRB, and others of all serious adverse events as required in the protocol. The Principal Investigator (or Protocol Chair) will provide information with respect to adverse events and safe use of the study treatment (e.g., safety reports, Action Letters) to all participating investigators as soon as the information becomes available. Investigative sites within DF/HCC will report all serious adverse events directly to the DFCI Office for Human Research Studies (OHRs).

#### 5.6.2 Anticipated Reactions

Since completion of the LEFT-BC questionnaire is voluntary, it is foreseeable that the use of the questionnaires may heighten the awareness of lymphedema and possible symptoms.

Additionally, assessment with BIS is voluntary and may increase awareness of lymphedema and cause distress regarding the potential development of the condition. Use of the device is considered safe and has regulatory clearance in the United States to “support the measurement of extracellular fluid volume differences between the arms to aid in the clinical assessment of unilateral lymphedema of the arm in women” (31). According to manufacturers, “the actual amount of electrical current passed through the body is imperceptible to most patients, is applied non-invasively and is applied over a brief period (less than 1 second)” (31).

#### 5.6.3 Reaction Management

In the event that a participant does feel an increased level of distress or discomfort, the social work team within the breast cancer center have confirmed their willingness and ability to provide additional counseling if necessary. [name], MSW has confirmed that she will be available to any patients who experience such adverse effects.

[name], LICSW  
P. [contact]  
[contact]

## 6.0 STATISTICAL ANALYSIS

### 6.1 Primary and Secondary Endpoints

The primary aims of the study are to assess the validity of BIS measurements by comparison with perometry and determine the relationships of BIS measurements to perometer measurements and to self-reported symptoms. The secondary aims will be to compare diagnostic criteria for lymphedema for each assessment method, assess the natural history of lymphedema using BIS, and determine a threshold for intervention using BIS. Thus primary endpoints will subsist in volumetric and BIS measurements of each arm at the baseline examination and during follow-up visits, as well as data captured by LEFT-BC questionnaires. The changes of arm volumes will be quantified using established RVC formula (26), and we will use a similar formula for quantification of BIS changes after evaluating the statistical distribution of BIS measurements.

### 6.2 Sample Size and Statistical Power

The sample size will be determined with the prospect of primary aim of this study, i.e, to evaluate the correlation between arm volume changes measured by perometry and quantified using RVC formula (26) and using relative changes of impedance measured by biimpedance spectroscopy (BIS). We want to evaluate this correlation for all subjects enrolled, and separately, for a subgroup of those subjects who develop lymphedema with  $RVC \geq 5\%$ . The first analysis will evaluate overall agreement between these two techniques and the second analysis will evaluate agreement between assessment of lymphedema grade by both techniques. We plan to quantify the relationship between these two measurement methods using Kendall's tau coefficient (34).

We chose to use a non-parametric correlation coefficient to account for a possible non-linear form of the relationship between the two measurements, and for a possible non-normal distribution of BIS measurements. We expect a moderately high correlation between these measurements,  $\tau = 0.50$ . The choice of sample size is motivated by a need to evaluate the correlation with sufficient precision rather than by a hypothesis test: we want to obtain a lower bound of 95% confidence interval for the estimate of tau of no less than 0.2 in the LE group and of no less than 0.42 overall. We assume that 10% of enrolled subjects will develop lymphedema with  $RVC \geq 5\%$ . Furthermore, we expect that up to 20% of paired measurements may be missing due to non-compliance or technical problems.

Sample size calculations are based on approximate confidence intervals for Kendall's tau (35). The minimum number of measurements, to attain the required precision in the LE group is n=16; however, accounting for missing data we need to enroll 20 patients with LE and 200 patients overall. We thus expect to have 160 non-missing pairs of measurements overall, this allows us to determine Kendall's tau with 95% confidence interval from 0.426 to 0.567.

Of note, patients that are enrolled pre-operatively and subsequently undergo bilateral breast surgery, rendering them ineligible for the study, will not be counted towards the overall accrual goal of 200 subjects.

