### 2.2 Secondary Objectives:

- Compare diagnostic criteria for lymphedema correlating with each assessment method

-Define the natural history of lymphedema and determine a threshold for intervention using BIS

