### 6.7 Analysis plan

The statistical analysis in this study will subsist in 1) calculating the Kendall's correlation coefficient with 95% confidence intervals for each time point, separately for all subjects and in the subgroup with  $RVC \geq 5\%$ , 2) plotting graphically the relationship between changes in arm volumes and BIS measurements, by time point, 3) calculate overall Kendall's tau stratifying by time point, i.e., evaluating concordant and discordant pairs within each time point only (35), 4) determining the change of BIS measurements

corresponding to RVC=5% of volumetric measurements, 5) calculating area under ROC curve, for predicting volumetric RVC $\geq$ 5% using BIS measurements, and tabulating diagnostic indices including specificity, sensitivity, positive prognostic value, 6) evaluating diagnostic characteristics of lymphedema diagnosis based on BIS using 3 sigma method, and 7) assessing the association between patient-reported symptoms and each measurement method (using area under ROC and other diagnostic criteria). We will also evaluate the statistical distribution of BIS measurements and based on the shape of the distribution determined if BIS changes are better captured as absolute or as relative differences.

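### Kendall's tau in the RVC≥5% subgroup measures rank association and cannot support the agreement on lymphedema grade that Section 6.2 claims for it

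*Combined protocol and SAP*

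**What the plan says.** Section 6.2 sets out two analyses of perometry against BIS, one in everyone enrolled and one "separately, for a subgroup of those subjects who develop lymphedema with" RVC of 5% or more. It names one statistic for both: "We plan to quantify the relationship between these two measurement methods using" Kendall's tau. It then interprets them. The first is said to address overall agreement; for the subgroup, "the second analysis will evaluate agreement between assessment of lymphedema grade by both techniques".

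The subgroup drives the design. At an expected tau of 0.50, the wish for a lower 95% limit of at least 0.2 gives 16 pairs, which becomes 20 patients after 20% missing data and 200 patients at a 10% lymphedema rate.

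On grade itself the documents give:
- **RVC:** mild (5 to <10%) and moderate (10 to 20%) bands, which are the randomization groups of the companion intervention protocol (Section 1.2.2 and Appendix 8.1.5).
- **BIS:** one threshold, three or more standard deviations from the norm (Section 1.2.1). No BIS grades appear anywhere.

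Section 2.2 lists as a secondary objective: "Compare diagnostic criteria for lymphedema correlating with each assessment method". Section 6.7 item 1 repeats the tau analyses without mentioning grade. Items 4 to 6 plan the BIS change that corresponds to RVC=5%, the ROC area with sensitivity, specificity and positive predictive value for RVC≥5%, and "evaluating diagnostic characteristics of lymphedema diagnosis based on BIS using 3 sigma method".

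**The concern.** Agreement on grade means that the two methods put the same patient in the same category, so it depends on where each method draws its boundaries. Tau counts pairs of patients whom the two methods order the same way or the opposite way, and no boundary enters that count. Any increasing rescaling of the BIS change, or any shift of a BIS grade limit, leaves tau exactly as it was. The 5% RVC limit affects the subgroup tau only by selecting who is in it.

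One side of the comparison is also missing: with a single BIS threshold there is no BIS grade for the RVC grade to agree with.

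At stake is how a primary-aim result is read. Section 6.2 gives the subgroup tau a meaning that it cannot carry. Whatever its value, the plan's own text would license a statement about grade agreement, and no other analysis in the plan would test that statement.

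**Working it through.** **1. The plan's own figures.** Inputs from Section 6.2: tau 0.50, target lower limit 0.2, missing 20%, lymphedema rate 10%. I used the bivariate-normal variance of tau with ρ = sin(π×0.50/2) = 0.707:

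Var = [2/(n(n−1))] × [1 − τ² + 2(n−2)(1/9 − 4·asin(ρ/2)²/π²)]

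At n=16 the SE is 0.141. On the arcsine scale this is 0.141/√(1−0.25) = 0.163, so the lower limit is sin(0.524 − 1.96×0.163) = 0.203, and n=16 is the minimum that meets the target. The raw scale gives 15 and Fisher z gives 18. Then 16/0.8 = 20, 20/0.10 = 200 and 200×0.8 = 160. The chain reproduces. At 160 pairs these same methods give about 0.418–0.424 to 0.572–0.576, close to the stated 0.426 to 0.567. A z-scale variance of about 0.36/(n−4) matches both the stated interval and the 16. The sample-size arithmetic is not in dispute here.

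**2. Tau against grade agreement (constructed example).** Take 16 patients with RVC 5, 6, …, 20% and BIS change an increasing function of RVC, so that tau = 1.0. Split RVC at 10%: 11 patients are moderate and 5 mild. Suppose, as an assumption, that BIS also had one mild/moderate boundary, and move only that. Kappa = (p_o − p_e)/(1 − p_e).

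| BIS boundary, as RVC equivalent | Tau | Same grade | p_e | Kappa |
|---|---|---|---|---|
| 10% | 1.0 | 16/16 = 100% | 0.570 | 1.00 |
| 6% | 1.0 | 12/16 = 75% | 0.664 | 0.26 |
| 14% | 1.0 | 12/16 = 75% | 0.477 | 0.52 |
| 18% | 1.0 | 8/16 = 50% | 0.383 | 0.19 |
| 25% (nobody moderate on BIS) | 1.0 | 5/16 = 31% | 0.313 | 0.00 |

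The largest possible tau is compatible with kappa anywhere from 0 to 1.

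**3. The same point for the yes/no cut-off (assumed model).** The documents give no rate at which BIS flags patients, so 2%, 10% and 30% are assumptions. Assume bivariate normality, overall tau 0.50 (ρ = 0.707) and 10% with RVC≥5%. P(both) is the joint upper-tail probability.

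| BIS flags | P(both) | Sensitivity = P(both)/0.10 | BIS-positives with RVC<5% | Kappa, all patients |
|---|---|---|---|---|
| 2% | 0.0143 | 0.14 | (0.02−0.0143)/0.02 = 28% | 0.21 |
| 10% | 0.0474 | 0.47 | (0.10−0.0474)/0.10 = 53% | 0.42 |
| 30% | 0.0826 | 0.83 | (0.30−0.0826)/0.30 = 72% | 0.31 |

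One value of tau fits all three rows. Patients in the fourth column are outside the subgroup unless they reach RVC≥5% at another visit. They are inside the all-subject tau and Section 6.7 items 4 to 6.

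**4. Range restriction.** Under the same assumed model, an overall tau of 0.50 falls to about 0.23 among the 10% with the highest RVC. A low subgroup tau could therefore reflect the narrowed RVC range rather than poor grading, so the label can mislead in either direction.

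**5. What Section 6.7 adds on grade.** Items 4 to 6 all concern a single cut-off. No item cross-classifies RVC bands against BIS categories, and none names an agreement measure for grade.

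**The case against.** The strongest reply is that this is loose wording. The same paragraph of Section 6.2 speaks of correlation and of a relationship between the methods, and Section 6.7 item 1, the operative text, makes no claim about grade. Section 1.2.1 also explains that ohms and millilitres cannot be compared directly, which is a good reason for a rank statistic. All of this is fair, and tau is a sensible measure of association. It does not rescue the sentence in Section 6.2: categories need no common unit, and the sentence assigns an interpretation to the analysis that sized the study.

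Two stronger readings are tempting, and the documents do not support them:

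- *A reader might infer that the plan never examines patients positive on BIS alone.* It does. Items 4 to 6 of Section 6.7 are not confined to the subgroup, so these patients enter through specificity and predictive value. A BIS cut-off that flagged very few or very many patients would show up there.
- *A reader might infer that the trial will report the methods as agreeing while they classify patients very differently.* That is a prediction. The planned yes/no indices would reveal such a discrepancy at the diagnostic threshold, and most of the table in step 3 restates quantities that the plan will produce anyway.

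It is also fair that a full grade comparison is not available today. The RVC bands are borrowed from another protocol and BIS has two levels, so kappa is undefined on the resulting 3×2 table. That limits the remedy and confirms that the promised analysis has no definition behind it.

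**Conclusion.** The point holds, confined to grade. The subgroup tau shows whether perometry and BIS order patients alike. It cannot show that they assign the same grade, and no BIS grade exists to compare. This follows from the definition of tau and needs no distributional assumption. The example in step 2 gives the size: at tau 1.0, agreement on grade can lie anywhere from 31% to 100%.

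The figures in step 3, including the 28% to 72% of BIS-positives with RVC<5%, rest on assumed normality and assumed flag rates and are illustrations only. The yes/no diagnostic comparison is planned and unaffected, and so are the sample-size figures. This is worth correcting because the change is cheap and the sentence governs how a primary-aim result will be read.

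**What to change.** 1. **Section 6.2:** describe both tau analyses as rank association between RVC and BIS change, and remove the claim of agreement on grade.
2. **Section 6.7:** add one table per time point, in all patients, of RVC band (<5%, 5 to <10%, ≥10%) by BIS positive or negative. Do this at the 3-SD threshold and again at the cut-off derived in item 4. Report the proportion BIS-positive in each band with a 95% CI.
3. **Kappa:** report it only for the 2×2 table (RVC≥5% by BIS positive). Use a weighted kappa only if ordered BIS grades matching the RVC bands are prespecified.

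The cost is wording plus one table per time point from data already collected, with no added patients or visits. Intervals will be wide in the upper bands, since only about 16 to 20 lymphedema patients are expected in total and fewer may be at or above 5% at any one visit. As an illustration, 8 of 16 BIS-positive has an exact 95% CI of 0.25 to 0.75; if the 16 split evenly into two bands, 4 of 8 has 0.16 to 0.84. The table should therefore be presented as descriptive.

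### Is the lymphedema-subgroup precision target in 6.2 undermined because it assumes tau of 0.50 there and is not tied to a named estimate?

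*Combined protocol and SAP*

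**What the plan says.** Section 6.2 plans two correlation analyses: one in all subjects, and one "for a subgroup of those subjects who develop lymphedema" with RVC of at least 5%. It describes the purpose of the latter thus: "the second analysis will evaluate agreement between assessment of lymphedema grade by both techniques". The planning value follows without distinguishing the two groups: "We expect a moderately high correlation between these measurements", with tau = 0.50. The stated aim is precision, not a hypothesis test, and the lower 95% limit is to be "no less than 0.2 in the LE group and of no less than 0.42 overall".

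The plan assumes that 10% of subjects develop LE and allows for missing data: "we expect that up to 20% of paired measurements may be missing due to non-compliance or technical problems". It then states: "The minimum number of measurements, to attain the required precision in the LE group is n=16". From this come 20 LE patients, 200 enrolled and 160 complete pairs overall, with an interval of 0.426 to 0.567.

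Section 6.7 item 1 calculates Kendall's "correlation coefficient with 95% confidence intervals for each time point, separately for all subjects and in the subgroup with" RVC of at least 5%. Item 3 adds an overall "tau stratifying by time point, i.e., evaluating concordant and discordant pairs within each time point only". Section 6.4 also stratifies the analysis on follow-up time.

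**The concern.** Two conditions behind the LE target appear unsecured.

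- **The value of tau.** The plan gives no reason for expecting 0.50 in a group chosen for high RVC. Restricting the range of one variable usually lowers a correlation, and with 16 pairs there is almost no room for a lower value.
- **The estimate.** Section 6.7 computes the subgroup tau visit by visit. It does not say whether membership means ever reaching 5% or being at or above 5% at that visit, and item 3 is not stated to cover the subgroup. If membership were judged at the visit, 16 pairs would rarely be available.

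The target also drives accrual: the overall limit of 0.42 alone would need fewer patients than 200. At stake is interpretation. A low subgroup tau with a wide interval could be taken as poor grading of lymphedema by BIS, when selection on RVC and small numbers would give the same picture.

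**Working it through.** **Inputs (6.2).** Tau 0.50; 95% confidence; lower limits 0.2 (LE) and 0.42 (overall); 10% LE; 20% missing pairs. The variance formula is not printed, so two candidates were tried.

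**Candidate 1: sine relation with Fisher's z.** Take r = sin(π·tau/2), form atanh(r) ± 1.96/√(n−3), and transform back by (2/π)·asin(tanh(·)). At tau 0.50, r = 0.7071 and atanh(r) = 0.8814.
- n = 160: half-width 1.96/√157 = 0.1564; interval 0.426 to 0.567. The plan's interval is reproduced.
- n = 16: half-width 1.96/√13 = 0.5436; 0.8814 − 0.5436 = 0.3378; tanh = 0.3255; lower limit 0.211.
- n = 15: lower limit 0.198, so the minimum is 16, as the plan states.

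**Candidate 2: tanh(atanh(tau) ± 1.96·√(0.36/(n−4))).** The constant 0.36 is fitted to the plan's interval, so only the result at n = 16 is a real check.
- n = 16: 0.5493 − 0.3395 = 0.2098; lower limit 0.207.
- n = 15: 0.192. The minimum is again 16.

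The alternative variance 0.437/(n−4) gives 0.418 to 0.574 at n = 160, which is not the plan's interval. It would need 18 pairs, not 16.

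**Accrual chain.** 16/0.80 = 20 LE patients; 20/0.10 = 200 enrolled; 0.80 × 200 = 160 pairs. The overall limit of 0.42 alone needs 138 to 140 pairs, and 138/0.80 = 172.5 and 140/0.80 = 175, so 173 to 175 enrolled. The LE target does set the total.

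**Margin.** The smallest subgroup tau that meets 0.2 is 0.492 (candidate 1) or 0.495 (candidate 2) at 16 pairs, and 0.460 at 20 pairs. Across variance formulas the value at 16 pairs runs from 0.48 to 0.52. At the front sheet's goal of 270, 270 × 0.10 × 0.80 = 21.6 pairs, and about 0.45 suffices.

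**Effect of selection on RVC.** These are assumed models, all with overall tau 0.50 and 10% LE; the documents give no data to choose between them.

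| Model | Subgroup tau |
|---|---|
| Normal, selection and tau at the same visit | 0.23 |
| Right-skewed swelling, same visit | 0.33 to 0.60 |
| Normal, ever-LE over 3 to 8 visits, tau at one fixed visit, stable swelling | 0.22 to 0.24 |
| Same, 25% of true swelling variance visit-specific | 0.36 to 0.38 |
| Same, 50% | 0.46 to 0.47 |
| Same, 80% | 0.54 to 0.56 |

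For 16 pairs, candidate 1 gives these intervals: tau 0.2, −0.14 to 0.49; 0.3, −0.03 to 0.56; 0.4, 0.08 to 0.63; 0.5, 0.21 to 0.70.

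**Which estimate.** Section 6.2 defines the group by subject. Combined with 6.7 item 1, that means one pair per LE patient at each time point: 80% of 20 = 16, parallel to 80% of 200 = 160. An at-visit definition would leave about 2 to 8 pairs per visit under the normal ever-LE model. At 8 pairs, even tau 0.50 gives a lower limit of 0.00 (candidate 1) or −0.04 (candidate 2). That reading sets aside the wording of 6.2.

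**The case for a change.** The strongest case for a change is this. The 0.2 target raises enrolment from about 175 to 200, so its basis ought to be stated. Tau in a group selected on RVC can be far below 0.50; under the simplest normal model it is 0.23, and 16 pairs then cannot give a lower limit of 0.2. Even the number of pairs is uncertain: if 10% develop LE, the chance of fewer than 16 LE pairs is 46% with 160 evaluable patients and 14% with 200. Because 6.2 presents the subgroup analysis as a test of grading, a weak result could be misread.

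Part of this stands. Section 6.2 gives no reason for 0.50 in the subgroup, and no sentence links the 0.2 target to item 1 of 6.7. The rest carries less weight:

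- The lowest subgroup values come from bivariate normality, whereas 6.2 chose Kendall's tau because the BIS measurements may not be normal and the relation may not be linear. Some skewed models put the value above 0.50.
- A shortfall in LE cases about half the time is what planning on an expected count means. It is not specific to this plan.
- Fewer pairs at chemotherapy or radiation visits affect the overall 160 as much as the LE group.
- Tau among patients with lymphedema is the quantity the plan wants. A restricted range makes it smaller, but the estimate is not thereby wrong.

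The one substantive alternative would tie the target to the 4-8 week verification visit in 5.3, where both devices are used. Under stable swelling and equal device error (variance 0.414 each), tau there is 0.33 against 0.23 for same-visit selection. With perometer error variance of 0.10 and overall tau still 0.50, the comparison shrinks to about 0.25 against 0.23. If the visit-specific swelling is redrawn, the verification visit gives 0.45 to 0.46 at the 50% share and 0.49 at 80%. Ever-LE at a fixed visit gives 0.46 to 0.47 and 0.54 to 0.56, which is as good or better. Verification visits also fall at different follow-up times, which cuts across the stratification in 6.4.

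**Conclusion.** No change is needed. At the plan's own tau of 0.50, 16 pairs meet the 0.2 limit (0.211 or 0.207) and 15 do not, so the stated minimum is correct. The thin margin, a needed subgroup tau of about 0.49, is a property of any minimum sample size. Whether the true subgroup value lies above or below that cannot be settled from the documents: the assumed models run from about 0.2 to 0.6.

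The remaining gap is an unexplained planning value and a missing cross-reference between 6.2 and 6.7. An analyst who follows 6.2 will define membership by subject and report each subgroup tau with its number of pairs and its interval, and that interval will show whatever precision was obtained. No decision rule depends on 0.2, and the front sheet records accrual as closed with its goal met, so rewording the precision statement would not alter the data or the estimates.

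This rests on inferred variance formulas, since the plan's own is not printed, and on reading the LE group as patients who ever reach RVC of 5%. A report of the subgroup result should still note that selection on RVC and few pairs can lower tau without BIS grading poorly. That is ordinary care in interpretation.
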